Intervention	All individuals residing in study localities will receive vector control preventative measures as per program. In the TPE arm, all individuals in the Target Area will receive dihydroartemisinin-piperaquine (DP) once daily for 3 days with the first dose taken no later than 5 weeks from the index case presentation (goal within one week). Individuals in RACD Target Areas will be tested by RDT and taken to the nearest health facility for treatment as per program operating procedures.
Evaluation methods	
The primary outcome measure of incidence will be obtained routine surveillance data. Secondary outcomes will be measured through Target area-level surveys:
 
1) Blood surveys. At the time of enrollment of a new Target area in RACD arm and at study conclusion in both arms (LAMP, QT-NASBA, serology, genotyping). DBS collected in incident cases as part of routine surveillance will also be utilized for genotyping.
 
2) Feasibility measurements: Coverage of RACD or TPE in the target population, serious adverse event (SAE) reports, costing of every 10th RACD and TPE event, pill count in TPE arm.
 
3) Acceptability assessment. Focus group discussions with TPE study participants and RACD/TPE surveillance team members.

Sample size	The sample size is based on the number of study localities that experienced at least one incident case of malaria in the previous season. Within 77 randomized localities, we expect that 63 localities will have an incident case of malaria and receive an intervention. For the primary objective, we hypothesize that TPE will be more effective than RACD. At the current sample size the study is powered to detect a difference in cumulative incidence if incidence in the TPE arm is reduced 50% compared to the RACD arm. Incidence will be measured at the locality level and among the at-risk population, or all individuals in an enumeration area (EA) where at least one case was identified (expected to be approximately 55928 among total study population of 211,189, or a harmonic mean of 656 per locality (41,328 effective population). Secondary outcomes of seroprevalence and prevalence will be measured on individuals residing in Target Areas (total N=5400) with a harmonic mean of 60 persons receiving intervention per locality (3780 effective population).
Primary outcome	Incidence of malaria cases

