Study participants will be recruited starting with index cases that are identified through a Case report/Case investigation system. After a laboratory confirmed index case is identified at a health facility, the health worker completes an Immediate Notification Form investigation (Appendix B) and reports the case through the country's toll-free Immediate Disease Notification System (977). The NMCP Surveillance Team is notified by an SMS text. A Surveillance Agent visit the health facility to collect the DBS, RDT, and slide, and visits the home of the index case within 48 hours and to administer a questionnaire and capture GPS coordinates, as part of the case investigation (Appendix C). Also, if a DBS was not collected by the health facility at the time of presentation, the surveillance agent also collects a DBS.

If the index case resides in a study locality, that neighborhood or Target Area will become enrolled in the study. During intervention resident enrollment, the study staff will begin recruiting study participants from the home of the index case, and then move on to neighboring households. On the first visit, the team will map the location of the index case and visualize the 200 or 500 meter radius on google maps while in the field. The team will attempt to enroll all individuals residing within 200 or 500 meters, depending on whether that Target Area has been randomized to receive TPE or RACE. On the second visit, the team must come at a time during which persons previously absent will be present (usually morning or late afternoon/early evening) and re-visit all households in which 100% coverage was not achieved. If 100% coverage is obtained, that Target Area intervention is complete. If not, on the 3rd visit, the team must also come at a time during which persons previously absent will be present (usually morning or late afternoon/early evening) and the study team must re-visit households in which 100% coverage was not achieved. If during this 3rd visit 30 individuals are not yet enrolled (participated in study intervention), the team will move onto the next closest house (but not beyond 500m) to screen individuals until at least 30 individuals are enrolled (but completing the screening in all individuals in that last household).

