14.1 Study population

Overall:

Based on the most recent census data, the overall population in the 77 study localities is estimated at 211,189 individuals. However we expect that some localities will have no incident cases and therefore not receive any intervention. In the previous two transmission seasons, only 63 of the 77 localities had at least one case. Our sample size calculations are further based on the expected at-risk population within the 63 localities, or EA that had at least one case in the previous three seasons, a total of 55,928 individuals. The size of the expected at-risk within localities varies greatly, therefore we used the harmonic mean of

population size in localities with at least one case (656 per locality) to represent the effective sample size of the study in calculations of the design effect.

Target Area:

As defined above in section 4.4, the Target Area for TPE localities is defined as all individuals residing within 200m of an index case that is detected in passive surveillance and resides in a TPE study locality, with individuals residing immediately beyond 200m included if a minimum of 30 enrolled individuals is not reached within 200m. The Target Area for RACD localities is defined as all individuals residing within 500m of an index case that is detected in passive surveillance and resides in a RACD study locality. Sample size calculations for the secondary outcome measures of seroprevalence and infection prevalence are based on the population of the Target Areas.

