For the primary analysis comparing incidence between the TPE and RACD arms, we will follow an intention-to-treat (ITT) approach. We hypothesize that cumulative incidence in the TPE localities will be lower than in the RACD assigned localities. For the initial ITT analyses, estimates of effect will be unadjusted for any variables other than intervention group. To check for possible contamination of effects by proximity to an index case treated with TPE, a second set of ITT analyses will be conducted adjusting for intervention group and distance of index case from an index case assigned to TPE. Outcomes are assessed at the individual level. Because of the clustered nature of the data, our modeling approach will also adjust for correlation of observations by locality for analyses using the overall sample and by locality and index case for analyses using the Target Area sample. Generalized estimating equations (GEE) will be used to perform the proposed primary analyses. GEE accounts for the correlation of persons within clusters and localities. GEE estimates are consistent even if the correlation structure is miss-specified, though GEE's statistical efficiency improves as the working correlation structure more closely approximates the actual correlation structure. Thus, several working correlation structures suitable for the study's design will be considered (e.g., unstructured, Autoregressive order 1, exchangeable). The QIC statistic will be used to select the final working correlation structure. Robust Huber-White "sandwich" standard errors will be used to obtain correct inferences even if

the chosen correlation structure remains slightly miss-specified. Alpha will be set at 0.05 for all planned comparisons.

Should the preliminary analyses reveal an imbalance in the baseline covariates between the TPE and RACD arms, a second set of models will be run for all primary analyses. Adjusted models will reweight the data (through inverse probability weighting, or targeted minimum loss based estimation) to recover effect estimates that reflect an equal distribution of baseline covariates.

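### The contamination-adjusted analysis of the primary outcome uses an index-case distance that has no value for over 99% of the at-risk population; it needs an exposure defined for everyone and fixed by the randomisation

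*Combined protocol and SAP*

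**What the plan says.** Under Primary Analysis, section 14.4 puts an intention-to-treat comparison adjusted for nothing but arm first. To check for contamination, it then plans a second set of models "adjusting for intervention group and distance of index case from an index case assigned to TPE". The same paragraph states that "Outcomes are assessed at the individual level" and that "Generalized estimating equations (GEE) will be used to perform the proposed primary analyses", with correlation by locality for the overall sample.

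Two other places describe the same adjustment differently. Section 4.4 speaks of distance from an index case whose surroundings received TPE, without limiting it to index cases. Secondary analyses in section 14.4 use distance to the nearest TPE-treated index case, for Target Area samples.

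On the denominator, the Study summary counts "all individuals in an enumeration area (EA) where at least one case was identified". Section 14.1 sizes it from "EA that had at least one case in the previous three seasons, a total of 55,928 individuals". The notes to Table 2 show that these are EA population totals, with total population taken from the 2007 census.

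On locations, section 6.2 has the surveillance agent visit the index case's home "to administer a questionnaire and capture GPS coordinates, as part of the case investigation". Table 4 and Appendices H and J add GPS for Target Area households. The protocol describes no location data for anyone else.

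**The concern.** A covariate in an individual-level model needs a value for every individual. Here the subject of the distance is the index case, and most people in the denominator are never index cases. The plan gives them no value, and its text on missing data (section 14.4, Preliminary Analyses) only promises to quantify how much is missing. Standard software would then drop every record without a value.

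Section 4.4 accepts that neighbouring localities in different arms may contaminate each other, and this model is the planned adjusted check of the primary result. If it runs only on cases, or on people mapped because of a case, it cannot show whether contamination diluted the effect. If the analyst has to choose a definition after the cases are known, the check is no longer pre-specified.

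**Working it through.** **1. Reproduce the denominator.** Table 2 has 63 localities with a non-zero expected at-risk population. Their sum is 55,928, and their harmonic mean, 63 / Σ(1/n), is 656.3. Both agree with section 14.1 (55,928 and 656).

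**2. Share with a value under the Primary Analysis wording.** Share = index cases / 55,928.

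| Index cases | Source | With a value | Without |
|---|---|---|---|
| 168 | 0.3% of 55,928, the mean of 0.4% and 0.2% (section 14.3) | 0.30% | 99.70% |
| 200 | section 14.1 | 0.36% | 99.64% |
| 268 | 134 per year × 2 (section 4.4) | 0.48% | 99.52% |
| 333 | Table 2 total, September 2012 to March 2015 | 0.60% | 99.40% |

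Against the full locality population of 211,189, 200 cases are 0.09%.

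**3. Share under the wider wording (section 4.4 and Secondary analyses).**
- Expected Target Area participants (section 14.1): 5,400 / 55,928 = 9.7%. Counting all 6,000 encounters: 10.7%.
- All listed residents: Appendices H and J are completed even where no one is home, and absent residents are still listed. With 53 residents within 200 m (section 4.4), 200 index cases and 10% overlap (section 14.1), 200 × 53 × 0.9 = 9,540, and 9,540 / 55,928 = 17%.

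The 17% leaves out RACD residents between 200 m and 500 m, for whom the protocol gives no count, so it is not a ceiling. Whatever the share, these people have a location because a case arose near them, and the mapping radius differs by arm (200 m for TPE, 500 m for RACD).

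**4. What a complete-case fit would contain.** Table 6 counts only cases after the first reported case in a locality. With one first case in each of 63 localities, 200 − 63 = 137 index cases are events.
- First cases removed: every remaining outcome is 1, so no incidence contrast can be estimated.
- First cases kept as non-events: the modelled proportion is 137 / 200 = 68.5%, whereas 137 / 55,928 = 0.24%. The fit describes later cases relative to first cases, which is not incidence.
- All mapped residents kept: the sample was selected by the occurrence of cases, with a different radius in each arm.

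**5. Attaching the distance to EAs.** Everyone then has a value, and a Poisson GEE with an area-level distance fitted without difficulty in an illustrative simulation using assumed locality coordinates. Two problems remain.
- If the denominator is EAs with a case identified during the study, every TPE-arm EA contains a TPE index case. If that case counts, the distance is near zero throughout the TPE arm and positive in the RACD arm. If it does not count, the distance measures how closely TPE cases cluster, which is bound up with the outcome.
- In both arms the value depends on where cases arise after randomisation, which the intervention is meant to change.

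**The case against.** The strongest reply is that the EA reading is natural. The denominator is made of EAs with at least one case, each such case is geolocated, and the distance can be carried to everyone in the EA. Only a rule for EAs with several index cases would be missing. Complete-case deletion is not written in the plan either. And contamination is also examined descriptively: section 14.4 reports distances between TPE and RACD index cases and counts RACD index cases within 2 km of a TPE one.

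Much of this stands, and it rules out several stronger readings that a reader might infer.
- The model is not inherently impossible to fit; an area-level distance can be fitted.
- Distances are not obtainable for index cases alone, because Target Area households are mapped.
- Index cases are not all events, because the first in each locality is excluded from the outcome.
- A TPE index case's distance need not be to itself. Secondary analyses refer to proximity to another TPE index case, although the primary text leaves the point open.

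The EA reading does not rescue the rule, however. It appears nowhere in the plan, no other way of giving non-cases a value is stated, and it brings in the dependence on arm and on later cases shown in step 5. The descriptive counts show where contamination could occur, but they do not adjust the incidence comparison.

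**Conclusion.** The second, contamination-adjusted analysis of the primary outcome is wrong as written. Its covariate has a value for about 0.3% to 0.6% of the at-risk population under the Primary Analysis wording, and for roughly 10% to 17% under the wider wording. In both cases it exists only for cases or for people mapped because of them. The EA version can be computed but is a poor adjustment variable.

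A reader might infer that the primary result itself is compromised. The documents do not support that: the unadjusted intention-to-treat comparison comes first and does not use the distance.

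The shares rest on the protocol's expected counts, and the 17% also on the assumptions in step 3. The statement that an EA-level distance would largely track arm follows from the Study summary's definition of the denominator. It is not quantified, because the documents give no coordinates. It would be weaker if EAs were chosen by their earlier cases, as in section 14.1, since some would then have no study case.

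**What to change.** Replace the covariate in section 14.4, Primary Analysis, with an exposure that every denominator unit has and that the randomisation fixes. One suitable choice is whether each EA lies within 2 km of a TPE-randomised locality, or how far it lies from one, measured from the EA boundary or centroid. The 2 km figure is borrowed from section 14.4, where it is a distance between index cases, so its use as a buffer should be stated as a choice.

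Use it as a sensitivity analysis only, in one pre-specified form:
- let the exposure act within the RACD arm; or
- exclude RACD EAs within 2 km of a TPE-randomised locality.

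Keep index-case distances as description, and align section 4.4 and the Primary and Secondary analyses text of section 14.4.

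The cost is a change of wording and one geographic calculation. It assumes that EA geography is available; Table 2 mentions shapefiles only as the source of locality names. A share of each EA's population within 2 km should not be specified, because locations within EAs are not documented. The measure is coarser than household distance. Proximity to a TPE locality is also not the same as TPE delivery: section 14.1 expects cases in only 63 of the 77 localities, so 77 − 63 = 14 would receive no intervention. The exclusion form loses some RACD EAs, and the documents do not allow that number to be estimated.

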1.3 Reactive case detection (RACD)

For elimination, active surveillance in the communities around passively detected index cases, reactive surveillance or reactive case detection, is recommended as a strategy to identify secondary cases and hot

spots.[2-4] However, re-active surveillance can be low yield, labor-intensive, and costly.[4] Microscopy is being replaced by antigen-based rapid diagnostic tests (RDTs) that provide convenience but have limitations in the sensitivity to detect low parasite density and non-falciparum infections.[5, 6] PCR offers markedly improved sensitivity, but it requires hours of processing time, sophisticated technical skill, and expensive equipment to perform. Loop mediated isothermal amplification (LAMP) offers the sensitivity of PCR and is easier to perform but the requirement that samples be performed in a laboratory limit its usefulness for population level screening and treatment.

Household members and neighbors around index cases harbor infection

In Swaziland, reactive case detection involves the screening of household members and neighbors residing within 500 meters of the index case. Preliminary data from reactive case detection in Swaziland show that reactive case detection is a useful strategy to find asymptomatic infections and hot spots. From September 2012 to April 2014, 74 additional infections were identified by LAMP in households and neighbors of 263 index cases, resulting in a 28% increase in the detection of infections. Residence near the index case was associated with a higher risk of infection. Residing within 100 meters of index case was associated with a 4.6 higher odds (95% CI 2.0 to 10.6) of infection compared to a baseline OR of 1.0 at 201-500m. Travel outside Swaziland and Mozambican nationality were associated with infection. However, excluding these individuals resulted in a similar finding: residing within 100 meters of index case was associated with a 4.2 higher odds (95% CI 1.7 to 10.4) of infection compared to a baseline OR of 1.0 at 201-500m (Figure 3).

[figure not shown]

Figure 3. LAMP positivity by distance from index case

Challenges with reactive case detection

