115000	MANZINIMKHIWENIKa-KhuphukaKa-Bheni	1	8	0	8	2	2755	1408	1408
432000	LUBOMBODVOKODVWENIMalindzaSikhuph e	2	6	2	8	1	3526	2920	2293
404000	LUBOMBODVOKODVWENISitekiKhushweni	2	5	4	9	5	1773	799	799
349000	LUBOMBOTIKHUBAMaphungwaneMhlabub ovu	1	9	1	10	5	2172	1115	542
150000	HHOHHOMHLANGATANEMhlangataneZiny ane	1	12	2	14	6	5869	2328	1745
179000	HHOHHONTFONJENIEmvembiliMvembili	1	13	1	14	4	1456	689	689
440000	LUBOMBOLOMAHASHALomahashaLomaha sha	1	5	10	15	4	2485	1960	1573

420000	LUBOMBOLOMAHASHAShewulaNduma	1	13	4	17	7	3894	3043	3043
481000	LUBOMBONKILONGOBig- BendVillages, Ka- Goboyane	1	2	15	17	14	890	418	418
415000	LUBOMBOLUGONGOLWENISiteki TownSiteki Town	2	9	13	22	6	4796	2377	2377
436000	LUBOMBOLOMAHASHALomahashaNkalash ane	1	22	3	25	3	4154	2307	1886
473000	LUBOMBOSITHOBELAKa- NgcamphalalaMahlabatsini	1	35	6	41	20	5011	2222	2222
Totals:			236	97	333	108	211189	71661	55928

Unique Locality Name generated using names of Region, Constituency, Name1 and Name2 from Shapefiles.

Risk ranks 1 to 3 (highest risk being risk rank 1) assigned by NMCP according to historical and recent transmission.

Secondary case data based on LAMP data from reactive case detection, shown but not used for randomization as trigger for the study intervention, and primary outcome measure for the study is only based on incident cases.

Total population data from 2007 census data.

Historically at-risk population calculated as population of enumerations areas with recent and historical transmission.

Expected at-risk population calculated as population of enumerations areas with recent cases (sept 2012-mar2015).

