4.4 Target Areas

The Target Area will be defined for TPE localities as all individuals residing within 200m of an index case that is detected in passive surveillance and resides in a TPE study locality, with individuals residing immediately beyond 200m included if a minimum of 30 individuals are not enrolled within 200m. This Target Area size was selected based on the existing RACD data whereby the mean number of individuals screened per index case was 32.

The Target Area will be defined for RACD localities as all individuals residing within 500m of an index case that is detected in passive surveillance and resides in a RACD locality. The malaria surveillance team will be trained to focus on maximizing coverage within the immediate 200m radius around the index case. This Target Area size was selected based on the current RACD policy in Swaziland.

Based on collected data on missing individuals, the estimated total number of individuals residing within 200m of an index case is 53. Thus, coverage to date for RACD has been 60%. However return visits do not typically occur at off hours (mornings and evenings). Moving forward, at least one return visit must occur during off-hours to ensure better capture and to maximize the sample size.

If a subsequent index case is reported in a target area (identified either through health facilities or RACD (all secondary cases identified in RACD become index cases)), the RACD intervention will not be repeated within 5 weeks (per current national policy). For the TPE arm, the intervention will not be repeated within 8 weeks or more than twice within the past year (DP drug insert recommends no repeat course within 8 weeks, and no more than 2 courses within one year).

Target Areas that reside on the border between two localities that were randomized to different arms will receive the intervention according to the locality randomization of the index case. For outcome measures, some contamination of the intervention arm's effect may occur if a neighboring locality is randomized to a different intervention. In the analysis we will adjust for distance from an index case for whom the surrounding area received TPE intervention. It will not be necessary to adjust for distance from an area where RACD was conducted because RACD is the current standard of care in all receptive areas of the country.

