Based on equation 4 from Hayes and Bennett International Journal of Epidemiology 1999;28:319-32

Assumes that population is only those in the EAs that have at least one case.

Sample size calculation based on harmonic mean of population size.

Table 8. Detectable reductions in seroprevalence given varying assumptions about prevalence in the RACD arm

# Total localities with at least one index case	# localities per arm	Number assessed per locality (n)		Outcome proportion		Km (coeff of variation)	Z beta	Power
		RACD	TPE	RACD (π_0)	TPE (π_1)			
46.6	23.3	60	60	3.00%	1.35%	0.9	0.84	80%
62.3	31.2	60	60	2.40%	1.18%	0.9	0.84	80%
49.3	24.7	60	60	2.00%	0.83%	0.9	0.84	80%
50.8	25.4	60	60	1.50%	0.57%	0.9	0.84	80%

Based on equation 4 from Hayes and Bennett International Journal of Epidemiology 1999; 28:319-326

Assumes we are including only persons in the target areas in the denominator but evaluating at locality level

Assumes 3 per 100 is the background seroprevalence

Table 9. Sample sizes for primary and secondary aims.

Outcome	Result*	Actual sample size (Effective sample size, based on harmonic mean in clusters)
Primary aim		
Incidence	0.4% (RACD) vs. 0.2% (TPE)	55,928 (41,328)
Secondary aims (effectiveness)		
Exposure (seroprevalence)	2.4% (RACD) vs. 1.18% (TPE)	5400 not including index cases (3720)
Infection prevalence	n/a	5600 includes index cases
Time to first post-intervention incident case	n/a	55,928 (41,328)

Outcome	Result*	Actual sample size (Effective sample size, based on harmonic mean in clusters)
Proportion of imported incident cases	n/a	55,928 (41,328)
Transmission potential	n/a	Genotyping estimated to be performed in 800 index cases** and 35 infections from follow-up cross sectional survey
Secondary aims (feasibility)		
Coverage in TPE Arm	80% (95% CI: 77%-83%)	1782
Adherence in TPE Arm	80%	532
Prevalence of SAEs related to treatment	n/a	5400 not including index cases (3720)
Acceptability	n/a	5400 not including index cases (3720)
Cost	n/a	10 Target Areas/arm

*for some secondary outcomes, power calculations were not performed however effective sample size is shown.

** 200 index cases will be from the study area but an estimated 600 DBS that are already collected as standard surveillance from other parts of the country will also be used to characterize the background genotypes/transmission potential in Swaziland, as it relates to the transmission potential in the study areas.

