Subgroup analyses: Although there is limited power with our constrained sample size, we will describe summary measures of incidence and intervention effects for some specific subgroups of interest within our study area population. Of particular interest are those who did or did not have insecticide spraying of their household areas, strata of risk as determined by the National Malaria Control Program, and season of index case presentation.

Secondary analyses:

Assessments of secondary outcomes will also be conducted using GEE techniques to account for the clustered nature of the data collection as described above. Secondary analyses for prevalence and seroprevalence are restricted to individuals in the Target Areas who will be participating in blood testing surveys conducted towards the end of the study (expected mid 2017). As noted, for analyses of outcomes in the Target Area sample, clustering by both locality and index case area will be accounted for in the modeling approach. To account for possible contamination by proximity to another index assigned to the TPE arm, models will also include adjustment for distance to the nearest index case treated with TPE. Planned secondary analyses and hypotheses are as follows:

Hypotheses regarding the effectiveness of TPE compared to RACD:

1. Comparison of seroprevalence using antibodies to markers of recent exposure. Using the samples collected in the end-line survey near the end of the study (expected mid 2017), we expect that seroprevalence will be lower in the Target Areas receiving TPE than in those receiving RACD.
2. Comparison of prevalence of malaria infection. Using the samples collected in the end-line survey near the end of the study (expected mid 2017), we expect prevalence to be lower in the Target Areas receiving TPE than in those receiving RACD.
3. Comparison of proportion of incident cases that are imported. We expect that local transmission will be reduced by TPE and thus the proportion of subsequent cases imported will be higher in the TPE arm than in the RACD arm. This outcome will be summarized at the locality level and analyzed with locality as the unit of analysis.

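### For end-line seroprevalence and infection prevalence, section 14.4 adjusts for a post-randomisation, arm-related distance and names no unadjusted lead estimate, which costs precision and does not yield a contamination-free effect

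*Combined protocol and SAP*

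**What the plan says.** Section 14.4 treats the primary and the secondary outcomes differently.

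- **Incidence (Primary Analysis).** The order is explicit: "For the initial ITT analyses, estimates of effect will be unadjusted for any variables other than intervention group". A second set of analyses then follows, "adjusting for intervention group and distance of index case from an index case assigned to TPE".
- **Secondary outcomes (Secondary analyses).** The stated purpose is "To account for possible contamination by proximity to another index assigned to the TPE arm", and the rule is that "models will also include adjustment for distance to the nearest index case treated with TPE". No unadjusted estimate is named for seroprevalence or infection prevalence, and no order of analyses is given.
- **Section 4.4 (Target Areas).** A third wording appears, without condition: "In the analysis we will adjust for distance from an index case for whom the surrounding area received TPE intervention".

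The Preliminary Analyses paragraph of 14.4 also plans to describe distances between index cases of the two arms, and to count RACD index cases within 2 km of a TPE index case. That description is useful and is not in question.

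On power, section 14.3 gives a calculation for seroprevalence (2.4% against 1.18%). Table 9 has no result for infection prevalence; its footnote says that "for some secondary outcomes, power calculations were not performed however effective sample size is shown".

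**The concern.** An analyst who follows the Secondary analyses text literally would report the distance-adjusted arm coefficient as the result for both end-line outcomes. Three features make that a poor lead estimate.

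1. **The covariate is not a baseline variable.** Index cases and their treatment accrue during the trial, and section 14.1 expects fewer cases under TPE. Whether an area is treated also depends on the repeat limits in section 4.4.
2. **It is tied to arm by design.** Whole localities are randomised, so any other index case in a TPE resident's locality is itself a TPE case. A RACD resident's nearest TPE case must lie in another locality.
3. **It is not fixed.** The three passages switch between index cases *assigned* to TPE, index cases *treated* with TPE, and areas that *received* TPE. One measures from the index case and the others give no origin. Functional form and time window are not stated.

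What is at stake is the precision and the meaning of two secondary effectiveness results. Incidence is protected by its unadjusted lead analysis.

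**Working it through.** **1. The plan's own figure.** Table 8 gives 62.3 localities in total for 2.4% against 1.18%, with 60 people per locality and k = 0.9. The usual cluster formula is

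c = 1 + (1.96 + 0.84)² × [p0(1−p0)/n + p1(1−p1)/n + k²(p0² + p1²)] / (p0 − p1)².

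With the numbers in: 1 + 7.84 × [0.000585 + 0.000579] / 0.000149 = 62.3. That is a count per arm, where the table prints it as the total. This is a separate matter. It means that the stated 80% is not a sound base for a power-loss figure, so none is given here.

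**2. Is distance tied to arm?** Table 2 has 63 localities with at least one incident case. Of these, 23 had exactly one and 63 − 23 = 40 had more than one. In a TPE locality with several cases, the nearest other TPE case is usually local.

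**3. Cost in precision.** If R² is the squared correlation of arm and distance, the standard error is multiplied by about 1/√(1 − R²).

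- *From the documents:* Table 2 case counts; 200 index cases (14.1), of which 66 TPE (14.3), leaving 134 RACD; 5400/200 = 27 residents per index case; radii of 200 m and 500 m; 2.4% and 1.18%, a risk ratio (RR) of 0.49; coefficient of variation 0.9.
- *Assumed, because no map is given:* localities on a jittered grid with 3, 6 or 10 km spacing; index cases scattered by 10, 20 or 30% of the spacing; own index case excluded.

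R² came out at about 0.15 to 0.55 over these layouts. In one set it was 0.16 to 0.41 for linear distance, so the factor is 1/√0.84 = 1.09 to 1/√0.59 = 1.30. For log distance it was 0.19 to 0.53, so the factor is 1/√0.81 = 1.11 to 1/√0.47 = 1.46. Simulated trials with locality-clustered sandwich errors gave a rise of 6 to 36% (linear) and 6 to 46% (log). At 20% scatter the rise was 11 to 19%. The loss is largest when cases sit tightly within localities.

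**4. Direction of the shift.** Central assumed case: 6 km spacing, 20% scatter, true RR 0.49. Spillover to RACD residents decays as exp(−distance/2 km). The gradient makes risk proportional to locality case count to the power 0.25.

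| Mechanism | Unadjusted RR | Linear distance | Log distance |
|---|---|---|---|
| Spillover only | 0.536 | 0.573 | 0.581 |
| Gradient only | 0.492 | 0.475 | 0.454 |
| Both | 0.536 | 0.552 | 0.533 |

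Under spillover, the problem that the adjustment is meant to solve, the adjusted RR lies further from 0.49 than the unadjusted one. With both mechanisms the ratios to unadjusted are 0.552/0.536 = 1.03 and 0.533/0.536 = 0.99. Across all scenarios with both mechanisms the ratio ran from 0.93 to 1.06 (linear) and from 0.83 to 1.05 (log).

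**5. How firm is the gradient?** A Poisson regression of Table 2 secondary cases on log incident cases, with log incident cases as offset and robust errors, gives a slope of 0.19 (95% CI −0.03 to 0.41). Omitting two localities (41 incident and 20 secondary cases; 17 and 14) gives 0.03 (−0.24 to 0.30). The exponent of 0.25 lies inside the first interval but above its point estimate. The gradient is therefore an assumption.

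**The case against.** **The unadjusted-first order may be meant to carry over.** The Primary Analysis paragraph also sets the clustering rule for the Target Area sample, which serves the secondary outcomes, and the secondary text refers back to methods already described. This is a possible reading. The back-reference attaches to GEE and clustering, however, and no unadjusted estimate is named for these outcomes. A reader might infer that the plan intends to drop the unadjusted estimate. The documents do not show that either; they leave it open.

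**The distance is not wholly undefined.** This stands. A metric is given, and the stated purpose concerns another index case, which points to excluding the resident's own. One might argue that distance nearly duplicates arm because TPE residents live within about 200 m of their own index case. That depends on counting the own case, so it is not used here. Origin, form and time window remain missing.

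**Section 1.3 might seem to establish the gradient.** It reports that "Residence near the index case was associated with a higher risk of infection", but that is distance from a resident's own index case, within 500 m. It says nothing about risk across localities kilometres apart. The Table 2 proxy ("Secondary case data based on LAMP data from reactive case detection") lacks numbers screened and rests heavily on two localities.

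**Adjustment might be said to create a TPE benefit where none exists.** That appears only if the gradient is assumed and spillover is set to zero. It is at most illustrative. A precision figure for infection prevalence has the same standing: the available one used a risk contrast other than the 1.6% and 0.4% stated in 14.4.

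**Both outcomes are secondary**, and the plan itself treats them with caution. This stands and limits the weight of the point.

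**Conclusion.** The point holds as a gap in specification with a real but conditional cost. No lead estimate unadjusted for distance is named for the two end-line outcomes, and the covariate in the model is post-randomisation, related to arm and incompletely defined. Some loss of precision follows from the link with arm. Its size, roughly 6 to 46% on the standard error, depends on geography and functional form that the documents do not give. The adjusted arm coefficient cannot be read as the effect without contamination. Its direction of shift depends on the balance of spillover and any risk gradient, and the net shift in the central assumed case is only about 1 to 3%. Nothing here shows bias in a known direction, a false TPE benefit, a quantified loss of power, or any problem with the primary analysis.

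**What to change.** In 14.4 (Secondary analyses) and 4.4:

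- Name the intention-to-treat arm contrast unadjusted for distance, with clustering by locality and index case accounted for, as the lead estimate for end-line seroprevalence and infection prevalence.
- Keep the distance model as a labelled sensitivity analysis. Use one definition in 4.4 and in both parts of 14.4: index cases assigned to TPE, own index case excluded, and origin, functional form and time window stated.
- Report it beside the descriptive distances already planned under Preliminary Analyses, and state that its arm coefficient is not a contamination-free effect.

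The cost is wording; no new data are needed and no planned analysis is lost. The downside is that the lead estimate stays diluted by any spillover, which should be stated as a limit.
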